CTCAE Toxicity Grade	Management/ Action	
1 or 2	No change.	
3	 Hold treatment. If the toxicity resolves to grade ≤ 1 or to the baseline grade within 7 days, treatment may be resumed at the same level or the next lower dose, at the discretion of the investigator after discussion with the sponsor. Toxicity that does not resolve to grade ≤ 1 or to the baseline grade within 7 days requires dose reduction to the next lower dose level. 	
4	 Hold treatment. If the toxicity resolves to grade ≤ 1 or to the baseline grade within 7 days, treatment may be resumed, but dose will be reduced by one dose level from the level at which the toxicity was observed. If grade 4 toxicity occurs at the lowest dose of 200 mg/day, the patient should be discontinued from the study. 	

4.3.6 The lowest dose of pacritinib used in the study will be 200 mg/day. If toxicity persists despite dose reduction to 200 mg/day, the patient should be discontinued from treatment.

4.4 Dose Management Guidelines for Hematologic Toxicities:

- 4.4.1 Myelosuppression is an expected event in patients with MF. However, myelosuppression with associated complications such as fever, infection, or bleeding or myelosuppression that worsens during treatment (based on local laboratory values) must be reported as an AE.
- 4.4.2 Patients with myelosuppression may receive supportive care including transient use of granulocyte colony stimulating factor for the treatment of febrile neutropenia and transfusion as clinically indicated.
- 4.4.3 Patients receiving pacritinib are not allowed to receive hematopoietic growth factors such as erythropoietin for the treatment of anemia.
- 4.4.4 Patients with clinically significant worsening of myelosuppression (as judged by the investigator and based on local laboratory values) for more than 7 days or myelosuppression associated with infection or bleeding should have pacritinib dosing interrupted. Pacritinib may be restarted at a reduced dose once the toxicity has resolved to grade ≤ 2 or to the baseline grade and the complications of myelosuppression such as infection or hemorrhage have resolved.

4.5 Allogeneic graft:

Peripheral blood (PB) or bone marrow (BM) progenitor cells may be used in this study peripheral blood will be preferred.

4.6 **Preparative Regimen**:

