8.0 Adverse Events and Reporting Requirements

8.1 AEs during Pacritinib phase

The severity of the adverse events (AEs) will be graded according to the Common Terminology Criteria v4.0 (CTCAE). We will not capture expected Grade 1 and Grade 2 AEs. Grade 3 and 4 AEs will be collected and recorded in the medical record. Only Pacritinib-related adverse events and protocol specific data will be entered into PDMS/CORe. PDMS/CORE will be used as the electronic case report form for this protocol.

Events not included in the CTCAE chart will be scored as follows: General grading:

Grade 2: Moderate: discomfort present with some disruption of daily activity, require treatment.

Grade 3: Severe: discomfort that interrupts normal daily activity, not responding to first line treatment.

Grade 4: Life Threatening: discomfort that represents immediate risk of death

Causality Assessment

For the purpose of this study, events known to be caused by Pacritinib will be assessed as definitely related.

Events known to be caused by components of the transplant package and its direct consequences as well as those events known to be related to drugs used for the treatment of GVHD, infections and supportive treatment will be scored as unrelated.

When the relationship of the adverse event cannot be ruled out with certainty the AE may be considered possibly related.

The PI will be responsible for assessing the causality and will be final arbiter. Documentation of grade, onset/resolution date and attribution will be entered into the patient's medical record and signed by the PI.

Collection of adverse events

Collection of adverse events will reflect the onset and resolution date and maximum grade. Intermittent events should be labeled as such and followed until resolution. If a patient is taken off study while an event still ongoing, this will be followed until resolution unless another therapy is initiated. Pre-existing medical conditions will be recorded only if an exacerbation occurs during the active treatment period. Co-morbid events will not be scored separately.

Adverse events related to Pacritinib will be collected and recorded for the duration of active treatment plus 14 days.

List of expected adverse events related to Pacritinib: Occurring in >10% include:

1. Nausea, vomiting, diarrhea, dehydration

- 2. Anemia, thrombocytopenia
- 3. Fatique

Treatment Duration Definitions:

Active Treatment: patients receiving Pacritinib.

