All life-threatening or fatal events, that are unexpected, and related to the study drug, must have a written report submitted within **24 hours** (next working day) of knowledge of the event to the Safety Project Manager in the IND Office.

The investigator will inform CTI Biopharma of any SAE within 24 hours of being aware of the event via email and/or fax.

Unless otherwise noted, the electronic SAE application (eSAE) will be utilized for safety reporting to the IND Office and MDACC IRB.

Serious adverse events will be captured from the time of the first protocol-specific intervention, until 14 days after the last dose of drug, unless the participant withdraws consent. Serious adverse events must be followed until clinical recovery is complete and laboratory tests have returned to baseline, progression of the event has stabilized, or there has been acceptable resolution of the event.

Additionally, any serious adverse events that occur after the 14 day time period that are related to the study treatment must be reported to the IND Office. This may include the development of a secondary malignancy.

Reporting to FDA:

Serious adverse events will be forwarded to FDA by the IND Sponsor (Safety Project Manager IND Office) according to 21 CFR 312.32.

Adverse events known to be related to SOC ALLO TP will not be recorded in PDMS.

List of most common expected adverse events related to SOC ALLO TP:

- 1. Infections in the presence or absence of neutropenia: fungal, bacterial and or viral infections.
- 2. Fever: Non-neutropenic or neutropenic without infection
- 3. Acute graft versus host disease (aGVHD): most commonly manifested by skin rash, diarrhea and abnormal liver function tests could also present with some degree of fever, upper gastrointestinal symptoms (nausea and vomiting) mucositis and eye dryness.
- 4. Gastrointestinal (GI tract): the GI tract manifestations could be not only due
- 5. to direct damage from the preparative regiment but also be a manifestation of GVHD or infections. Therefore, the time course and its presentation are crucial when assessing these as adverse events. Nausea/vomiting, mucositis, diarrhea when presented within first 7 to 10 days most likely will be related to the preparative regimen.
- 6. Skin rash: not related to GVHD could be caused by chemotherapy used for the preparative regimen or antibiotics used a supportive treatment.
- 7. Transaminitis: liver function test elevation.

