- 8. Pulmonary events: not related to CHF most likely caused by drug injury or infection. These could present with a pneumonitis pattern manifested with shortness of breath, pulmonary infiltrates on chest radiograph, sometimes accompanied by fever and cough and progress to acute respiratory insufficiency and a diffuse bilateral alveolar pattern.
- 9. Cytokine Storm/ engraftment syndrome: most likely caused by released cytokines.
- 10. Hemorrhagic cystitis: not related to chemotherapy agents used in the proposed preparative regimen is most likely caused by viral infection.
- 11. Thrombotic thrombocytopenic purpura (TTP).
- 12. Veno-occlusive Disease of the Liver (VOD): could be caused by Busulfan. Some antimicrobial agents have been also incriminated in its development.
- 13. Fluid overload due to hydration required for conditioning regimen, blood product transfusions and or IV alimentation
- 14. Graft failure.
- 15. Chronic GVHD.

- 16. For the purpose of this study, the following events would not be considered adverse events and would not be recorded in the database:
 - a. Flu-like symptoms not associated with infection
 - b. Abnormal laboratory findings considered associated to the original disease
 - c. Isolated changes in laboratory parameters such as electrolyte, magnesium and metabolic imbalances, uric acid changes, elevations of ALT, AST, LDH and alkaline phosphatase.

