- Cardiac: QTc prolongation has been reported in association with pacritinib therapy. A post-hoc review of the patients in the phase 1-2 Studies SB1518-2007-001 and SB1518-2008-003 identified 9 patients with at least one reported QTc exceeding 500 ms; all but one were treated at a pacritinib dose of ≥ 400 mg QD. Therapy was continued in most of these patients for extended periods of time after the observations of QTc prolongation. In addition, pre-study cardiac history was noted in 7 patients, and 8 patients were taking concomitant medications associated with QTc prolonga-tion. Other cardiac TEAEs and ADRs were rare in all pacritinib-treated populations. Based on these observations, investigators are advised to exclude any patient with a baseline QTc > 450 ms and to perform routine ECG monitoring during treatment. For patients with identified changes in treatment-emergent ECG abnormalities or other cardiac events, study drug may be interrupted or the dose may be reduced per protocol.
- Hepatic: Animal studies suggest that pacritinib treatment may cause dose-related hepatotoxicity. There has been little evidence of hepatotoxicity in clinical trials to date. Significant increases in aminotransferases have been observed infrequently and have not been accompanied by concomitant increases in bilirubin. Most reported hepatic toxicities were seen in the myeloid population. No instances of hepatic dysfunction meeting Hy's Law criteria have been observed. Hepatic function (AST/SGPT, ALT/SGOT, alkaline phosphatase, and total bilirubin) will continue to be assessed at frequent intervals during treatment with pacritinib.
- **Renal**: Animal studies suggest that treatment may cause dose-related renal toxicity. To date, little impact on renal function has been observed in human clinical trials. Assessment of renal function (creatinine, BUN, sodium, potassium) will be undertaken frequently in patients participating in clinical trials of pacritinib.

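### Item 16 of Section 8.0 has no limit by phase, grade or attribution, so isolated, non-serious grade 3-4 enzyme or electrolyte changes on pacritinib can be left out of the adverse event database

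*Combined protocol and SAP*

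**What the plan says.** The list headed "List of most common expected adverse events related to SOC ALLO TP" in Section 8.0 ends with item 16, which opens by referring to the study as such and says that "the following events would not be considered adverse events and would not be recorded in the database". Three kinds of event follow:

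- 16a: flu-like symptoms without infection.
- 16b: "Abnormal laboratory findings considered associated to the original disease".
- 16c: "Isolated changes in laboratory parameters such as electrolyte, magnesium and metabolic imbalances, uric acid changes, elevations of ALT, AST, LDH and alkaline phosphatase".

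Section 8.1, which governs the pacritinib phase, says "Grade 3 and 4 AEs will be collected and recorded in the medical record". It sends pacritinib-related events to the PDMS/CORe database and collects them during active treatment and for 14 days afterwards. It does not mention item 16.

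Section 4.4.1 says that "myelosuppression that worsens during treatment (based on local laboratory values) must be reported as an AE". Section 9.4 gives the hepatic risk: "Animal studies suggest that pacritinib treatment may cause dose-related hepatotoxicity". It adds that marked aminotransferase rises in patients have been infrequent and came without a rise in bilirubin. Section 6.0, under Secondary Analyses, plans a descriptive tabulation of AE rates, with a separate summary for patients who take pacritinib but are not transplanted.

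**The concern.** An exclusion placed in the definition of an adverse event acts before any rule about which adverse events to collect. If item 16 applies while patients are on pacritinib, the grade 3-4 rule in Section 8.1 never reaches an isolated ALT, AST or electrolyte change, because that change is not an AE to begin with.

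Safety is a secondary objective, and the AE rate is the only safety parameter that the analysis section names. The Background also gives lower organ toxicity as one of the ways in which pacritinib before transplant might help. A hepatic laboratory rate that is too low because of a recording rule would therefore mislead on a question the trial asks. A reader of the final table could not tell a true absence of such events from an absence by definition.

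**Working it through.** No figure in the plan bears on this point, so the check sets the provisions side by side.

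1. **Wording of item 16.** The opening phrase refers to the study. No phase is named, no grade is exempted, and 16c has no attribution test. The one qualifier in 16c is that the change be isolated. The parameters are given as examples; bilirubin and creatinine are not among them.

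2. **Placement of item 16.** It is the last number in the list of transplant-related events, so a transplant-only intent is possible. Three provisions leave that reading with little to do:
   - Section 4.1.3 stops pacritinib 21 days before the preparative regimen, and Section 8.1 closes collection of pacritinib-related AEs 14 days after the last dose. Collection therefore closes 21 - 14 = 7 days before conditioning starts.
   - Section 8.0 separately keeps AEs known to be related to the transplant out of PDMS, and item 7 of the same list already names liver enzyme elevation. A transplant-only 16c would largely repeat this.
   - Item 16b concerns the original disease, which is not specific to transplant.

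3. **Against Section 8.1.** Take an isolated, non-serious grade 3 ALT rise judged related to pacritinib. Under 8.1 it is collected, kept in the medical record as an AE and entered in PDMS/CORe. Under item 16 it is not an AE and is not entered. Both instructions cannot be followed.

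4. **Against Table 3 (Section 4.3).** Table 3 calls for treatment to be held for a grade 3 or 4 pacritinib-related nonhematologic toxicity. The same ALT rise could therefore interrupt study drug and leave no AE record that explains the interruption.

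5. **Against Section 9.4.** Aminotransferase rises without a bilirubin rise are the form in which the hepatic signal has appeared so far. That pattern is easily classed as isolated, so the qualifier does not protect it.

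6. **Item 16b against Section 4.4.1.** Section 4.4.1 makes worsening myelosuppression on laboratory values reportable. Item 16b removes laboratory findings attributed to the disease. The two clash only if a worsening count is attributed to myelofibrosis. That attribution is open to the investigator, since 4.4.1 itself describes myelosuppression as expected in this disease.

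7. **Other routes of capture.** SAEs go to the IND Office whatever their attribution, and important medical events may be classed as serious. Chemistry is drawn monthly and on Day 14 of Cycle 1 (Section 5.2), so the values exist. However, an isolated grade 3 laboratory change need not meet any seriousness criterion, and Section 6.0 names no separate analysis of laboratory values.

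8. **Size.** The documents give no rate for isolated, non-serious grade 3-4 enzyme or electrolyte changes. The Background says that only anemia or thrombocytopenia (16%) exceeded 10% at grade 3 or higher, and Section 9.4 calls significant aminotransferase rises infrequent. These statements suggest a low rate but do not fix one.

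**The case against.** The strongest reply is that item 16 was meant for the transplant phase only. It sits in the transplant list, and the pacritinib phase has its own heading and rules, which never refer to it. That reading cannot be excluded. It does not remove the problem, because the text does not state it and, as shown above, it leaves the item almost redundant.

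It is also fair to say that 16c reaches only isolated changes, that serious events are reported regardless, and that 16b on its own terms removes findings due to the disease and not drug toxicity. All of this stands and narrows the point.

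A reader might infer more, in three ways:

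- **That hepatic and electrolyte toxicity would go wholly unrecorded.** It would not. Serious events and abnormalities that are not isolated are still captured, and the laboratory results remain available.
- **That excluding electrolyte and magnesium changes hides the QTc risk.** The documents do not link the two. Item 16 does not exclude QTc prolongation, and an EKG is done at baseline, monthly on pacritinib and after its completion.
- **That the gap bears on veno-occlusive disease after busulfan.** Transplant-related events are kept out of PDMS by a separate sentence, whatever item 16 says.

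**Conclusion.** The concern holds in a limited form. On a literal reading, isolated, non-serious grade 3-4 enzyme or electrolyte changes on pacritinib can be omitted from the AE database and so from the tabulated AE rates. This contradicts Section 8.1, can leave a Table 3 hold without an AE record, and affects the hepatic pattern that Section 9.4 describes. The tension between 16b and Section 4.4.1 is weaker, since it depends on how a worsening count is attributed.

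The direction is clear: where item 16 is applied to the pacritinib phase, the recorded rate can only be too low. The size is unknown, and a count of missing events would need a rate that the documents do not supply. The conclusion assumes that sites may follow item 16 as worded. If they all read it as transplant-only, nothing is lost in practice, but the plan does not ensure that. The primary endpoint is not affected.

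**What to change.** Reconcile Sections 4.3, 4.4.1 and 8.1 with item 16 by amendment:

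- State that item 16 applies only from the start of conditioning. For patients who never reach conditioning, it would then not apply at all.
- State in Section 8.1 that, from the first dose of pacritinib to 14 days after the last, two kinds of laboratory finding are recorded as AEs: any grade 3-4 abnormality, and any abnormality of whatever grade that leads to a hold, reduction or stop of pacritinib.

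This changes recording only. It adds no test, because the chemistry panels and blood counts are already scheduled, and it leaves dose management as it is. The cost is a short amendment and a small amount of extra data entry. For patients already treated, the entries could be completed from results on file.

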9.0 Background Drug Information

9.1 Pharmacologic Class of Pacritinib: JAK2-FLT3 inhibitor

9.2 Formulation

For use in clinical studies as an oral agent, pacritinib is supplied as size #0 hard gelatin capsules with gray bodies and red caps. Capsules contain 100 mg pacritinib (free base) and the following inactive ingredients: microcrystalline cellulose NF, polyethylene glycol 8000 (PEG 8000) NF, and magnesium stearate NF. The capsule gelatin is bovine derived.

Pharmacies at investigational sites will receive bottles with child-resistant closures containing 100 capsules (100 mg).

9.3 Storage Conditions

Drug product should be stored in the pharmacy, hospital, clinic, or warehouse at controlled room temperature, 20°C to 25°C (68°F to 77°F), with excursions allowed between 15°C to 30°C (59°F to 86°F). Patients should be instructed that storage temperatures for pacritinib in the home should be below 30°C (86°F). Unused or expired Pacritinib will be disposed per MDACC Investigational Drug policy,

9.4 Observed Risks

The adverse effects observed in toxicity studies, as well as data from phase 1 and 2 clinical studies in patients with advanced MF, AML, and lymphoma:

- Hematologic: Reversible myelosuppression; leukopenia, neutropenia, thrombocytopenia, and anemia have been observed; these events are common in hematologic malignancies and may not be related to pacritinib administration. Thrombocytopenia, anemia, neutropenia, and leukopenia ADRs were more common in lymphoid than myeloid patients. Patients participating in clinical trials of pacritinib will be monitored frequently for myelosuppression. Provisions for interruption of treatment and dose reduction in the event of myelosuppression are outlined in clinical trial protocols.
- Gastrointestinal: Treatment with pacritinib is associated with dose-related diarrhea and nausea. Vomiting, abdominal pain, abdominal distension, anorexia, and constipation have also been reported to be related to pacritinib administration. Diarrhea and vomiting ADRs were more common in myeloid studies than lymphoid studies, but the reverse was true for constipation. Nausea was the same in both populations. Antiemetic and antidiarrheal medications should be prescribed prophylactically to control symptoms. Fluid and electrolytes should be replaced as needed to prevent dehydration. Pre-existing nausea, vomiting, and diarrhea should be adequately controlled before beginning therapy. Patients

- with significant GI symptoms despite optimal supportive care may have study drug interrupted or have the dose of study drug reduced per protocol.
- Cardiac: QTc prolongation has been reported in association with pacritinib therapy. A post-hoc review of the patients in the phase 1-2 Studies SB1518-2007-001 and SB1518-2008-003 identified 9 patients with at least one reported QTc exceeding 500 ms; all but one were treated at a pacritinib dose of ≥ 400 mg QD. Therapy was continued in most of these patients for extended periods of time after the observations of QTc prolongation. In addition, pre-study cardiac history was noted in 7 patients, and 8 patients were taking concomitant medications associated with QTc prolonga-tion. Other cardiac TEAEs and ADRs were rare in all pacritinib-treated populations. Based on these observations, investigators are advised to exclude any patient with a baseline QTc > 450 ms and to perform routine ECG monitoring during treatment. For patients with identified changes in treatment-emergent ECG abnormalities or other cardiac events, study drug may be interrupted or the dose may be reduced per protocol.
- Hepatic: Animal studies suggest that pacritinib treatment may cause dose-related hepatotoxicity. There has been little evidence of hepatotoxicity in clinical trials to date. Significant increases in aminotransferases have been observed infrequently and have not been accompanied by concomitant increases in bilirubin. Most reported hepatic toxicities were seen in the myeloid population. No instances of hepatic dysfunction meeting Hy's Law criteria have been observed. Hepatic function (AST/SGPT, ALT/SGOT, alkaline phosphatase, and total bilirubin) will continue to be assessed at frequent intervals during treatment with pacritinib.
- **Renal**: Animal studies suggest that treatment may cause dose-related renal toxicity. To date, little impact on renal function has been observed in human clinical trials. Assessment of renal function (creatinine, BUN, sodium, potassium) will be undertaken frequently in patients participating in clinical trials of pacritinib.
- General: Additional adverse effects commonly reported during pacritinib administration have included infections, fatigue, asthenia, peripheral edema, pyrexia, and rash. Infectious ADRs were more common in lymphoid patients, while the other adverse effects were more common in myeloid patients. Bleeding and bruising complications have been reported, most of which were low grade and generally more common in the myeloid population than in the lymphoid population. Patients participating in clinical trials of pacritinib will be monitored closely for these adverse effects.

No reproductive or developmental toxicity studies have been performed; therefore, the effects of pacritinib on female and male fertility are unknown. If fertile, both males and females must agree to use effective birth control. Women of childbearing potential must use highly effective methods of birth control for the duration of study treatment and for 12 months after last dose of study drug. The contraceptive methods considered highly effective are intrauterine devices and hormonal contraceptives (contraceptive pills, implants, transdermal patches, hormonal vaginal devices, or injections with prolonged release).

No drug-drug interaction studies have been conducted with pacritinib. In vitro studies indicate that pacritinib has no significant potential to inhibit or induce CYP450 isozymes and has no significant involvement with p-glycoprotein mediated transport. Pacritinib is believed to be metabolized by CYP3A4. Therefore, caution is advised when considering the coadministration of potent inhibitors of CYP3A4 in conjunction with pacritinib. Specific exclusions are outlined in the protocols for human clinical trials of pacritinib.

